- For measurement of delivered dose, daily effluent volume (in mL) will be recorded from the Prismaflex System history screen. In the Prismaflex software, the starting time for the charting interval will be set (eg, at 8:00 am) and the volumes and doses will be stored for each day starting at that time. The effluent volume together with the patient's weight will be used to calculate delivered dose (mL/kg/hour). Note that *daily* weight will need to be obtained and recorded/entered each morning (eg, at 8:00 am) in the "System Tools" screen for determination of both prescribed and delivered dose as part of standard clinical practice for each patient receiving CRRT.
- For both study arms Systemic ionized blood calcium concentrations will be measured at baseline and initiation, 1 hour after initiation of CRRT (post-randomization) and then at 6 hour intervals up to 120 hours of CRRT (see Appendix 1).
 - For the Prismocitrate 18 Arm, the systemic ionized calcium must be measured 1 hour prior to the initiation of study CRRT. If initiation ionized calcium is less than 0.9 mmol/L, the investigator must correct the serum level to greater

than 0.9 mmol/L in order to begin CRRT. This corrected systemic ionized calcium will be considered the patient's initiation value (see Appendix 1).

- For Prismocitrate 18 Arm Only Post-filter blood iCa will be measured 1 hour after initiation of CRRT (post-randomization) and then at 6 hour intervals up to 120 hours of CRRT (see Appendix 1).
- Blood total calcium concentrations will be measured at baseline, initiation, 1 hour and every 6 hours during the 120 hour Treatment Period and at 120 hours or end of the Treatment Period from the initiation of study CRRT in each. In conjunction with simultaneous systemic iCa concentrations, the total calcium/iCa ratio (both measurements in mmol/L) will be determined (see Appendix 1).
- Serum electrolytes (sodium, potassium, chloride, phosphate, and magnesium, anion gap) and base excess will be measured at baseline, initiation and at 6 hour intervals of study CRRT (post-randomization) up to 120 hours (see Appendix 1).
- Blood urea nitrogen (BUN) and serum creatinine measurements will be measured at baseline, initiation and twice daily (post-randomization) up to 120 hours of study CRRT (see Appendix 1).

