4.2 Secondary Objectives

The secondary objectives of this study are to evaluate the efficacy of Prismocitrate 18 in achieving appropriate anticoagulation through assessments of systemic and post-filter blood iCa concentrations, and to evaluate the efficacy of using Prismocitrate 18 in delivering the prescribed CRRT dose, with delivered dose based on total (daily) effluent volume and expressed as mL/kg/hour. Additionally, the safety profile will be evaluated through assessments of metabolic parameters, including serum bicarbonate, pH, base excess, iCa, total calcium, magnesium, chloride and other relevant serum electrolytes along with anion gap. The potential for the development of citrate accumulation will be evaluated specifically through assessment of the total calcium/iCa²⁺ ratio (both measurements in mmol/L), anion gap and base excess (along with pH). Finally, the potential for bleeding events (number, location, duration), and the number and type of blood transfusions along with the number of units infused will also be assessed.

From the functional perspective, another secondary objective is to complete training on administration of Prismocitrate 18 and demonstrate the understanding of the user groups on how to use the solution by passing an assessment at the end of training. The user groups who need to be assessed prior to use of Prismocitrate 18 in the clinical trial setting will be comprised of physicians, nurses, and other clinicians who may be part of prescribing, initiating, or modifying treatment during the 120 hours evaluation period.

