5.5.2 Secondary Efficacy Endpoints

Systemic and post-filter blood iCa concentrations will be assessed at baseline (systemic only), 1 hour and every 6 hours during the 120 hours Evaluation period and at 120 hours or end of the Evaluation period from the initiation of CRRT in each patient as indications of both the extent of calcium chelation prior to the CRRT filter and calcium restoration after the CRRT filter

Delivery of the prescribed CRRT dose will be based on daily recordings of both the effluent volume (in mL) and the patient's weight. These data will be used to calculate delivered dose (mL/kg/hour).

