13.3 Secondary Analysis

A descriptive summary of systemic and post-filter blood iCa²⁺ concentrations as assessed at baseline (systemic only), 1 hour and every 6 hours during the 120 hours evaluation period and at 120 hours or end of the Evaluation period will be provided by treatment group. This summary will use the number of subjects n, mean, standard deviation, minimum, median and maximum. Changes from baseline will be analyzed by the number of subjects n, mean and standard deviation and t-test or Wilcoxon rank sum test, as applicable.

The individual blood iCa²⁺ concentrations will further be displayed graphically over time for each of the two treatment groups.

A MMRM analysis will be deployed to evaluate differences between treatment groups in blood i Ca^{2+} concentrations that are collected at baseline, 1 hour and every 6 hours during the 120 hours Evaluation period and at 120 hours or end of the Evaluation period from the initiation of CRRT. The model will include the illness severity score APACHE II, baseline i Ca^{2+} concentration, treatment group and time point as fixed effects, and an interaction between time point and treatment group will be included in the model only if treatment effects differ statistically significantly over time (p < 0.01).

In addition, frequencies and percentages will be provided for $iCa^{2+} < 1.1 \text{ mmol/L}$ by time point and treatment group (threshold indicative of decrease in iCa^{2+} despite adequate calcium compensation).

Daily delivered dose and overall delivered dose (both in mL/kg/hour) will be summarized using the number of subjects n, mean, standard deviation, minimum, median and maximum, as applicable. Treatment exposure will be analyzed carrying out the same descriptive summary for the percentages of the prescribed dose actually administered to the patient.

Effluent rate is considered an appropriate surrogate for the CRRT dose. Therefore, prescribed and delivered CRRT dose will be derived as follows based on the University of Alabama at Birmingham Continuous Venovenous Hemodiafiltration Protocol¹² used in the study:

$$Q_E = Q_{PBP} + Q_D + Q_{FR} + Q_R$$

where Q_E is the effluent rate (mL/hour),

Q_{PBP} is the pre-blood pump infusion rate which is the Prismocitrate 18 flow rate (mL/hour),

Q_D is the dialysate flow rate (mL/hour),

Q_{FR} is the patient fluid removal rate (mL/hour), and

Q_R is the post-filter replacement fluid rate (mL/hour).

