If one of the rate is missing, effluent rate will not be able to calculate.

The prescribed dose (effluent rate) is calculated as:

Prescribed Effluent Rate = Body Weight \times 25 mL/kg/hr

If there are multiple records of effluent rate per day (e.g. due to infusion rate change) the average value will be used to calculate the delivered dose for that day.

The percentage of the prescribed dose actually administered to the patient will be calculated by dividing the actual effluent rate by the prescribed effluent rate. Differences between treatment groups in the percentage of overall prescribed dose actually administered will be assessed on a 5% significance level using a two-sided t-test or Wilcoxon rank sum test, as applicable. However, the statistical test will only be carried out conditional upon a significant test result for the primary endpoint at the time point of the interim analysis or final analysis. This hierarchical test procedure guarantees that the overall Type I error is controlled and preserved at a maximum of 5%.

The analysis of secondary efficacy endpoints will be carried out on the FA based on the randomized treatment groups (intent-to-treat principle).

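### SAP 13.3 derives the gated dose percentage from a flow-rate sum over weight × 25 mL/kg/hr, although both documents base delivered dose on recorded effluent volume and 25 is only the minimum prescription

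*SAP*

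**What the plan says.** **Volume basis.** SAP 4.2 states the objective "with delivered dose based on total (daily) effluent volume and expressed as mL/kg/hour", and Protocol 2.2 agrees. SAP 5.5.2 and Protocol 6.7.2 calculate the endpoint from daily effluent volume and weight. Protocol 5.2 gives the source: "For measurement of delivered dose, daily effluent volume (in mL) will be recorded from the Prismaflex System history screen".

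**Rate basis.** SAP 13.3 says "prescribed and delivered CRRT dose will be derived as follows" and then gives Q_E = Q_PBP + Q_D + Q_FR + Q_R. It adds two rules: "If one of the rate is missing, effluent rate will not be able to calculate", and "If there are multiple records of effluent rate per day (e.g. due to infusion rate change) the average value will be used". The prescribed rate is "Prescribed Effluent Rate = Body Weight" times 25 mL/kg/hr, and the percentage is "calculated by dividing the actual effluent rate by the prescribed effluent rate". Recorded effluent volume does not appear in 13.3.

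**Role of the percentage.** It is compared between arms at the two-sided 5% level, but only after a significant primary result. SAP 11 also reports treatment exposure with it. SAP 19 records that the test was added so that endpoints which might support labeling claims were pre-specified. SAP 12 declares no departure from the protocol.

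**The concern.** Three parts of the derivation do not match the quantity that both documents say is tested, namely the share of the prescribed dose that the patient received.

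1. **Numerator.** Protocol 5.2.2.2.1 uses the four-term sum to work out the rate to be prescribed. SAP 13.3 extends it to delivery. The sum has no volume or time term, so on the plain reading hours off CRRT do not lower it.
2. **Denominator.** Weight × 25 is the floor for prescribing (Protocol 5.2, 5.2.2 and 5.2.2.2.1), not what was prescribed for the patient. This holds however the numerator is read.
3. **Pre-blood-pump term.** SAP 13.3 equates Q_PBP with the Prismocitrate 18 rate. Control patients receive replacement fluid by that pump, at no less than 1000 mL/h (Protocol 5.2), and Q_R covers only the post-filter fluid.

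At stake is the only secondary efficacy comparison in the testing hierarchy. Protocol 1.2 expects Control patients to lose delivered dose through interruptions. That is the effect a volume-based measure captures and a sum of running rates does not.

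**Working it through.** **The plan's own figure.** Protocol 5.2.2.2.1: 90 kg × 25 mL/kg/h = 2,250 mL/h, which reproduces. No power or sample-size figure is given for the dose endpoint.

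**What the 13.3 sum measures.** Protocol 7.4.2 collects the component flow rates as prescription data, initial and changed. Two rules in 13.3 fit that source. Several records in a day are attributed to rate changes, and one missing component makes the result incalculable. A recorded volume would need neither rule. The plain reading is therefore a sum of rate settings.

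**Inputs.** Minimum prescribed dose 25 and minimum target delivered dose 20 mL/kg/h (Protocol 5.2.2.2.1). The prescription of 30 and all hours off circuit are assumptions; the documents give no distribution for either. The table assumes delivery at the prescribed rate while running and counts all four flows.

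**Formulas**, for prescribed dose D and h hours off in 24:
- share of own prescription = 100 × (24 − h)/24
- 13.3, plain reading = 100 × D/25
- volume over time, divided by weight × 25 = 100 × D × (24 − h)/24 ÷ 25

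| D (mL/kg/h) | h | Share of own prescription | 13.3, plain reading | Volume/time over weight × 25 |
|---|---|---|---|---|
| 25 | 4.8 | 80% | 100% | 80% |
| 30 | 0 | 100% | 120% | 120% |
| 30 | 6 | 75% | 120% | 90% |

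The first row is the protocol's pair, 20/25 = 80%, with the shortfall assumed to be all downtime (4.8/24 = 20%). In the last row delivery is 30 × 18/24 = 22.5 mL/kg/h. Even a volume-based numerator then gives 22.5/25 = 90%, so the denominator alone adds 15 points.

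**Pre-blood-pump term, Control arm.** A 70 kg patient prescribed the minimum has 70 × 25 = 1,750 mL/h, of which at least 1000 mL/h runs through the pre-blood pump. If Q_PBP is treated as missing, the rule in 13.3 gives no value. If it is set to 0, the result is at most (1,750 − 1,000)/1,750 = 43%. For the protocol's 90 kg example it is at most (2,250 − 1,000)/2,250 = 56%.

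**The case against.** **The numerator may not be a sum of settings.** SAP 13.3 does not define the actual effluent rate. Protocol 5.2 says the machine stores daily volumes and doses, SAP 5.5.2 keeps volume as the basis, and the cited CVVHDF protocol figure on which 13.3 builds is not shown in the text available here. A programmer could divide recorded volume by time. This stands, and it lowers certainty on the numerator. It would also remove the Q_PBP problem, since no sum would be used. It leaves the denominator untouched, and 13.3 does not state it.

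**A fixed denominator has a merit.** In an open-label trial the prescription is set and changed after randomization, so lower prescribing raises a percentage of the actual prescription. Weight × 25 avoids that. This is a good reason to report delivered dose against weight × 25 as well. It does not make that ratio the share of prescribed dose, which is the quantity that Protocol 8.5.2 and SAP 13.3 name for testing.

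**Sensible programming may fill the Q_PBP gap.** Appendix 2, footnote h, lists a PBP flow rate, which could be used for Control. That is plausible, but 13.3 says otherwise and should be corrected.

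**Inferences to avoid.** A reader might infer that 13.3 favors one arm. The documents do not support this, because the effects pull in different directions. Ignoring downtime could hide a loss in Control, a zero Q_PBP would understate Control, and prescribing above the minimum raises whichever arm does it. Protocol 5.2 allows local practice in both arms and gives no prescribing or downtime distribution. A reader might also infer that the Per Protocol Set is compromised. Its 80% dose criterion (SAP 6.2.2) is affected only if it uses 13.3, which is not stated.

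**Conclusion.** SAP 13.3 is inconsistent with SAP 4.2 and 5.5.2 and with Protocol 2.2, 5.2 and 6.7.2. Followed as written, it does not produce the percentage that the hierarchy is meant to test. It should be corrected before that test is run.

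Confidence is high for the inconsistency and the denominator. It is moderate for the plain reading of the numerator, because the actual effluent rate is undefined.

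For a single patient the error can be large: 80% becomes 100%, or 75% becomes 120% (90% with a volume-based numerator), under the assumed downtime and prescription. A Control value may be missing or cut to 43% if Q_PBP is taken literally. These are illustrations. The size and direction of any difference between arms cannot be derived from the documents. The test and the SAP 11 exposure summary are affected; the Full Analysis Set primary analysis is not.

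**What to change.** Rewrite the derivation in SAP 13.3 to agree with 5.5.2:

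- **Delivered dose:** recorded effluent volume ÷ (weight × elapsed hours), from study CRRT initiation to the patient's last study CRRT stop in the Treatment Period. Interruptions count in the hours, and partial charting days use their actual hours. State one rule, the same in both arms, for a first charting day that contains pre-study volume, and make it cover patients treated within a single charting day.
- **Prescribed dose:** the patient's recorded prescribed total effluent rate, initial and as changed, ÷ weight. Take the PBP flow rate in both arms from Appendix 2, footnote h, because Protocol 7.4.2 alone lists no Control rate for that pump. Time-weight where change times exist; otherwise apply a stated daily rule.
- **Q_PBP:** redefine it as the total pre-blood-pump rate in either arm.
- **Weight:** state one weight for numerator and denominator, reconciling Protocol 5.2 (daily) with 5.2.2.2.1 (at CRRT initiation).
- **Test:** compare delivered ÷ prescribed. Report delivered dose against weight × 25 descriptively, which also shows any arm difference in post-randomization prescribing.
- **Per Protocol Set:** state whether the 80% criterion uses this derivation.

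The cost is SAP wording, some programming and a few derivation rules. Effluent volume, daily weight, set start and end times, disruptions and prescription changes are already collected. The limits are that Protocol 7.4.2 lists no time for each change and that volumes are stored by fixed charting day; the stated rules deal with both. No dose or clinical rule changes.

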13.4 Exploratory Analyses

Not applicable.

13.5 Interim Analysis

The analysis described under 13.1 Primary Analysis will be carried out after 50% of patients have completed treatment. The purpose of the interim analysis is to evaluate the primary efficacy endpoint for overwhelming efficacy, or the need to adjust the sample size. If the primary analysis yields a statistically significant test result (p < 0.0087, critical value for clustered log rank test based on Bauer & Koehne procedure with no early stopping for futility) on the FA, and if further no safety concern or other considerations require continuation of enrollment, the study will be stopped for overwhelming efficacy. Otherwise enrollment of subjects will continue and the whole statistical analysis as described in this document will be carried out at the end of the study using Fisher's combination test (please see Section 13.1 Primary Analysis for details). This approach guarantees that an overall Type I error of 0.05 is preserved.

In order to re-assess the sample size for the subset of subjects recruited after the interim analysis, simulation studies will be run utilizing the p-value observed at the interim analysis (p₁). The re-assessment of the sample size will be carried out using the original assumptions for median circuit life times in the two treatment groups (in the Prismocitrate 18 and control group) and will target a conditional power of 90% for rejecting the null hypothesis given the observed results of the interim analysis.

13.6 Subgroup Analyses

No specific subgroup analyses are planned.

14. SAFETY AND TOLERABILITY

Parameters to be tabulated for safety include the following: AEs/SAEs; bleeding events and transfusions; serum bicarbonate, pH and base excess, blood total calcium, blood total calcium/iCa²⁺ ratio, and serum electrolytes; anion gap; vital signs, creatinine, blood urea nitrogen, and bleeding parameters.

Any statistical analysis of safety endpoints will be carried out on the FA based on the actual treatment groups.

14.1 Adverse Events (AEs)

The outcome/resolution of all AEs and SAEs will be determined by the Investigator and documented on the AE case report form (CRF)/SAE report form.

An overview of the number of subjects with at least one AE, at least one SAE, at least one study product-related AE, at least one study product-related SAE, and withdrawn due to SAE will be summarized (frequency and percentage of subjects).

An overview of the number of AEs, SAEs, study product-related AEs, and study product-related SAEs along with rates of events per subject treatment days will be tabulated.

The number of subjects with at least one AE (Serious and Non-Serious) will be summarized by MedDRA System Organ Class and MedDRA Preferred Term (frequency and percentage of subjects). The number of AEs (Serious and Non-Serious) and the rates of AEs per subject treatment days will be summarized by MedDRA System Organ Class and MedDRA Preferred Term. In addition, the number of subjects with at least one AE (Serious and Non-Serious) will be summarized by MedDRA System Organ Class, MedDRA Preferred Term and Severity (mild, moderate, severe) (frequency and percentage of subjects).

The number of subjects with at least one study-product related AE (Serious and Non-Serious) will be summarized by MedDRA System Organ Class and MedDRA Preferred Term (frequency and percentage of subjects). The number of study-product related AEs (Serious and Non-Serious) and the rates of study-product related AEs per subject treatment days will be summarized by MedDRA System Organ Class and MedDRA Preferred Term. In addition, the number of subjects with at least one study-product related AE (Serious and Non-Serious) will be summarized by MedDRA System Organ Class, MedDRA Preferred Term and Severity (mild, moderate, severe) (frequency and percentage of subjects).

Any subject-based analysis of AEs (e.g., number of subjects with at least one AE) will be based on the worst severity reported for the subject for the event analyzed. If, for example, a subject reports two mild and one moderate AE(s), in the subject-based analysis the event will be presented only once under moderate severity. Study product-related AEs will be considered those AEs classified as probably or possibly associated with the device or drug. AEs unrelated to study product will be considered those with a causality assessment of unlikely or not associated. If the relationship to the drug/device is not available or not assessable, the respective AE will be classified as study product-related.

Data listings for AEs and SAEs will contain MedDRA System Organ Class, MedDRA Preferred Term, diagnosis, start date, stop date, severity, action taken regarding study product, relationship to study product and outcome.

Adverse events reported between signing the ICF and first study treatment will be listed separately.

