4.4 Removal of Patient from Therapy, Assessment, or Study

Patients are considered withdrawn/prematurely discontinued from the study if their participation is discontinued before completion of the required evaluations as specified in the protocol Section 6.5. However, only the patient's individual treatment will be interrupted and the study will continue. Patients may be withdrawn/prematurely discontinued from the study for any of the following reasons:

- 1. Adverse event (AE) or serious adverse event (SAE).
- 2. Protocol violation/deviation (ie, the patient failed to meet protocol entry criteria or did not adhere to the protocol requirements).
- 3. Pregnancy.
- 4. Voluntary withdrawal (ie, patient's request).
- 5. Termination of the study.
- 6. Investigator's discretion.
- 7. Death.
- 8. Other [with reason noted on the electronic case report form (eCRF)].

The Investigator may terminate a patient's study participation at any time during the study if he/she judges it to be in the patient's best interest. If a patient is withdrawn from the study, the Study Monitor must be informed in the shortest possible time, regardless of the reason for withdrawal. In addition, a patient may discontinue his or her participation at any time during the study. If a patient's participation is discontinued, the reason(s) must be recorded in the source documents and on the eCRFs. If a patient discontinues for any reason, every effort should be made to perform all of the procedures that are scheduled for the End of Treatment visit. Patients who are withdrawn from the study will not be replaced. In addition, all SAEs, related or not, will be followed post-study treatment period for 30 days and until stabilized, resolved, or returned to baseline.

The patient's individual treatment will be interrupted but the study will continue if an event occurs that is considered by the investigators and/or the Sponsor as possibly

leading to a deficiency in the patient's treatment and is related to the use of Prismocitrate 18

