5.2.3 Monitoring of Therapy

Systemic iCa levels will be measured at baseline, initiation, and systemic and post-filter blood iCa levels will be measure 1 hour after initiation of study CRRT (post-randomization) and then every 6 hours thereafter and at 120 hours or end of Treatment Period. The pH and bicarbonate should be measured at baseline, initiation, and every 6 hours during the 120 hour Treatment Period and at 120 hours or end of Treatment Period. Health care professionals managing the patient should be instructed to notify the clinician immediately if the serum pH is < 7.20 or > 7.45, serum bicarbonate is < 15 or > 35 mmol/L, and/or the systemic blood iCa is < 0.9 or > 1.3 mmol/L.

Citrate metabolism may be impaired in patients with moderate to severe liver failure. The additional steps outlined below are needed to monitor specifically for the potential development of citrate accumulation, not only in these patients but in the entire study

population. Blood total calcium concentrations will be measured at baseline, initiation, 1 hour and every 6 hours during the 120 hour Treatment Period and at 120 hours or end of the Treatment Period from the initiation of study CRRT. In conjunction with simultaneous systemic iCa concentrations, the total calcium/iCa ratio (both measurements in mmol/L) will be determined as an indicator of citrate accumulation and health care professionals managing the patient should be instructed to notify the clinician for any value above 2. 1. Moreover, based on the clinical judgement of the managing physician, this threshold value should also prompt an immediate CRRT prescription change designed to correct the metabolic disturbance. One of the following prescription changes should occur:

- Decrease in the Prismocitrate infusion rate; or
- Increase in the BFR; or
- Increase in the dialysate flow rate

The effect of one of these changes should be assessed with ongoing monitoring of relevant clinical and laboratory parameters - if improvement does not occur within two (2) hours, the Prismocitrate infusion should be stopped.

When a total calcium/iCa ratio of more than 2.1 is reported, any one of the following abnormalities reported concurrently should heighten the clinical suspicion of citrate accumulation and reinforce the need to undertake the steps outlined above:

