5.9 Completion and Discontinuation

The number of completed and discontinued subjects along with reasons for discontinuation will be summarized. Individual reasons for study discontinuation will be listed.

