15. OTHER RELEVANT DATA ANALYSES/SUMMARIES

Individual data collected on initial treatment prescriptions and changes during the evaluation period, on dialysate, replacement solution, priming solution, calcium gluconate or calcium chloride used during the evaluation period will be provided in data listings. Likewise, detailed CRRT treatment information, Prismaflex M150 Set information, blood access information and CRRT machine and treatment modality will be listed.

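### The AE overview counts withdrawals only when the cause is an SAE, and no summary table shows AEs that led to stopping or reducing Prismocitrate

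*SAP*

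**What the plan says.** SAP Section 14.1 opens with a subject-level overview. Its items are any AE, any SAE, any product-related AE and, at the end, "at least one study product-related SAE, and withdrawn due to SAE will be summarized". It has no item for withdrawal due to any AE and none for an AE that led to a change in study product.

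The rest of Section 14.1 is broad. "The number of subjects with at least one AE (Serious and Non-Serious) will be summarized by MedDRA System Organ Class and MedDRA Preferred Term", with further tables by severity and as event rates. The same set is repeated for related events: "The number of subjects with at least one study-product related AE (Serious and Non-Serious) will be summarized by MedDRA System Organ Class". The AE data listings carry "severity, action taken regarding study product, relationship to study product and outcome".

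Elsewhere in the SAP:

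- Section 5.9: "The number of completed and discontinued subjects along with reasons for discontinuation will be summarized".
- Section 15 sends prescription data to listings: "Individual data collected on initial treatment prescriptions and changes during the evaluation period".

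In the protocol, the first withdrawal reason in Section 4.4 covers AEs as well as SAEs. Section 5.2.3 describes what follows a total calcium/iCa ratio above 2.1. Subject to the physician's judgement, one of three prescription changes is made. If there is no improvement within two hours, "the Prismocitrate infusion should be stopped".

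**The concern.** Protocol Section 1.2 names changes in electrolyte and acid-base balance as the main foreseeable risk of Prismocitrate, and the safety profile is a secondary objective (Section 2.2). Section 5.2.3 gives a pathway by which such an event can end the infusion. Nothing in that pathway requires the event to be serious or the patient to leave the study.

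How many patients had the product stopped or cut back because of an AE is an ordinary question for a Phase III safety section. As planned, the only AE-linked discontinuation count in that section is conditional on both seriousness and withdrawal. The typical patient on the Section 5.2.3 pathway may meet neither condition. A reader of the study report would have to count these patients by hand from listings.

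**Working it through.** No arithmetic bears on the main question; it is a matter of which outputs exist. The plan states no figure to reproduce. The check follows one hypothetical patient through the planned outputs.

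**Test case.** A Prismocitrate patient has a ratio above 2.1. A prescription change brings no improvement within two hours and the infusion is stopped. The investigator records a non-serious AE, and the patient completes the 30-day follow-up. Recording it as an AE is an assumption. Under Protocol Section 6.10 a laboratory abnormality qualifies if it needs medical intervention, leads to discontinuation from the study, or exceeds limits set by standard of care.

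| Planned output | Is the patient counted? | Is the stop of product visible? |
|---|---|---|
| AE overview (SAP 14.1) | Yes, as a patient with an AE | No: not an SAE, not withdrawn |
| System Organ Class, Preferred Term and severity tables (SAP 14.1) | Yes | No |
| Disposition (SAP 5.9) | Can be a completer | No |
| Exposure and reasons for ending circuits (SAP 11) | Yes, as exposure | Not as an AE-related stop |
| Laboratory thresholds (SAP 14.3) | Yes, when the ratio exceeds 2.1 | No |
| AE listings (SAP 14.1) | Yes | Yes, but as a listing |
| Prescription listings (SAP 15) | Yes | As a rate change, in a listing |

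Three rows need explanation.

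1. *Disposition.* Protocol Section 7.6 treats a patient as completing the study after up to 120 hours of study CRRT plus the 30-day AE follow-up. Early stopping of Prismocitrate therefore does not by itself make the patient a discontinuation. SAP Section 13.1 also provides for patients who remain under observation after a change of therapy. Filters used after a switch between arms stay in the primary analysis under the randomized arm, and switches to other therapies are censored. Protocol Section 5.2.1 does not allow cross-over, but the SAP plans for it and asks for no count of switches caused by an AE. When a patient does withdraw for an AE, Section 5.9 captures it, under a protocol reason that combines AE and SAE.

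2. *Circuit reasons.* Stopping or reducing the infusion need not end a circuit. Where a circuit does end, the examples of reasons in Protocol Section 7.4.7 are clotting, raised TMP, tests outside the ICU and device malfunction. That list is open-ended but names no AE category.

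3. *Table lists.* The later of the SAP's two lists numbers the AE tables 14.3.1.5 to 14.3.1.22, that is 22 − 5 + 1 = 18 tables. They are split by seriousness, relatedness, System Organ Class and Preferred Term, and severity. None is split by action taken, and neither is any AE table in SAP Section 18.

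**Source data.** Protocol Section 6.10 requires the actions taken to be recorded for each AE, and the SAP listing expects that field. The itemised AE eCRF content in Protocol Section 6.11 does not name it, and no categories are given. Flow-rate records (Section 7.4.2) name no reason for a change. They also contain routine titration: Section 5.2.2.2 allows steps of 100 mL/hour to hold post-filter iCa, and the effluent-rate and blood-flow subsections allow further adjustment.

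**The case against.** The strongest reply is that the plan already covers non-serious toxicity well. Non-serious AEs are counted by Preferred Term, severity and rate, both overall and when product-related. Withdrawals for an AE enter the disposition summary. The markers of citrate accumulation and acid-base disturbance have their own threshold tables. All of this is correct. A reader might infer from the overview that non-serious events leading to a change of Prismocitrate are tabulated nowhere; the documents do not support that. The events are tabulated. Their link to a product action is not.

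A second reply is that a change in Prismocitrate rate is a poor measure of harm, because the solution is a titrated replacement fluid. A patient managed instead through blood flow or dialysate flow would also be missed. This stands against using flow records as the source and against treating reduction as the main measure. It does not answer the missing count of AE-related stops. Nor should one infer that the protocol mandates reduction: it is one of three options, under clinical judgement.

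A third reply is that a reduction row has no counterpart in a Control arm that receives no Prismocitrate. This also stands, so that row can only be descriptive within one arm.

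Finally, the information is recoverable from listings wherever action taken is recorded. That limits the importance of the gap but does not remove it.

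**Conclusion.** The point holds as a gap in safety reporting. The overview's withdrawal item is narrower than the protocol's own withdrawal reason. No planned summary shows how many patients had Prismocitrate stopped or reduced because of an AE.

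No numerical size can be given, because the documents state no expected frequency of such events. A reader might be tempted to say that the SAE-withdrawal count understates toxicity by some factor. That does not follow: withdrawal from the study due to an SAE and stopping or reducing the infusion are different events, and a correct count of one is not an underestimate of the other.

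The conclusion assumes that at least some such episodes are recorded as AEs, and that some of those patients stay in follow-up. Neither table list names a separate disposition table, so the Section 5.9 summary presumably belongs in Table 14.1.1, Subject Overview. If that table were designed to count stops of study product separately from study withdrawal, part of the gap would close; the SAP does not say so. The change is worth making before the tables are final, but the primary analysis does not depend on it.

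**What to change.** In SAP Section 14.1, replace the SAE-withdrawal item with:

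- (a) patients with any AE leading to withdrawal from the study;
- (b) patients with any AE leading to permanent stop of study product or study CRRT.

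Report both by arm with n, % and a serious/non-serious split, and tabulate (b) by Preferred Term. For the Prismocitrate arm only, add descriptively:

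- (c) patients with any AE leading to reduction or interruption of study product.

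Derive these from the AE action-taken field, after confirming that the eCRF holds it and that its categories separate stop, interruption and reduction. Do not derive them from flow-rate changes. If the categories are coarser, state which rows can be supported.

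The cost is SAP wording and one or two extra descriptive tables, with no new data if the field is as the SAP implies. Sample size, alpha, power and conduct are unaffected, and no change to any clinical rule is proposed.
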